10 DEFINITIONS OF ADVERSE EVENTS, SUSPECTED ADVERSE DRUG REACTIONS & SERIOUS ADVERSE EVENTS

10.1 Adverse Event and Suspected Adverse Drug Reactions

An adverse event (AE) is any unfavorable and unintended sign (including a clinically significant abnormal laboratory finding, for example), symptom, or disease temporally associated with a study, use of a drug product or device whether or not considered related to the drug product or device.

Adverse drug reactions (ADR) are all noxious and unintended responses to a medicinal product related to any dose. The phrase "responses to a medicinal product" means that a causal relationship between a medicinal product and an adverse event is at least a reasonable possibility, i.e., the relationship cannot be ruled out. Therefore, a subset of AEs can be classified as suspected ADRs, if there is a causal relationship to the medicinal product.

Examples of adverse events include: new conditions, worsening of pre-existing conditions, clinically significant abnormal physical examination signs (i.e. skin rash, peripheral edema, etc), or clinically significant abnormal test results (i.e. lab values or vital signs), with the exception of outcome measure results, which are not being recorded as adverse events in this trial (they are being collected, but analyzed separately). Stable chronic conditions (i.e., diabetes, arthritis) that are present prior to the start of the study and do not worsen during the trial are NOT considered adverse events. Chronic conditions that occur more frequently (for intermittent conditions) or with greater severity would be considered as worsened and therefore would be recorded as adverse events.

Adverse events are generally detected in two ways:

Clinical → symptoms reported by the Subject or signs detected on examination.

Ancillary Tests → abnormalities of vital signs, laboratory tests, and other diagnostic procedures (other than the outcome measures: the results of which are not being captured as AEs).

If discernible at the time of completing the AE log, a specific disease or syndrome rather than individual associated signs and symptoms should be identified by the site Investigator and recorded on the AE log. However, if an observed or reported sign, symptom, or clinically significant laboratory anomaly is not considered by the site Investigator to be a component of a specific disease or syndrome, then it should be recorded as a separate AE on the AE log. Clinically significant laboratory abnormalities, such as those that require intervention, are those that are identified as such by the site Investigator.

Expected adverse events are those that are known to be associated with or have the potential to arise as a consequence of participation in the study. As noted earlier, the following problems were reported in Subjects taking SRX246 in Phase I studies: tachycardia, conjunctival hyperemia, upper abdominal pain, diarrhea, epigastric discomfort, gastroesophageal reflux, lip pain, nausea, vomiting, chest pain. Almost all of these were mild in intensity. The problems were not dose related.

Unexpected adverse events are those adverse events, the specificity or severity of which are not consistent with the current Investigators Brochure or package insert or described in the protocol. An unexpected, suspected adverse drug reaction is any unexpected adverse event that, in the opinion of the site Investigator or Sponsor, there is a reasonable possibility that the investigational product caused the event.

10.2 Serious Adverse Events

A serious adverse event (SAE) is defined as an adverse event that meets any of the following criteria:

1. Results in death.
2. Is life threatening: that is, poses an immediate risk of death as the event occurred.
 - a. This serious criterion applies if the study Subject, in the view of the site Investigator or Sponsor, is at immediate risk of death from the AE as it occurs. It does not apply if an AE hypothetically might have caused death if it were more severe.
3. Requires inpatient hospitalization or prolongation of existing hospitalization.
 - a. Hospitalization for an elective procedure (including elective PEG tube/g-tube/feeding tube placement) or a routinely scheduled treatment is not an SAE by this criterion because an elective or scheduled “procedure” or a “treatment” is not an untoward medical occurrence.
4. Results in persistent or significant disability or incapacity.
 - a. This serious criterion applies if the “disability” caused by the reported AE results in a substantial disruption of the Subject’s ability to carry out normal life functions.
5. Results in congenital anomaly or birth defect in the offspring of the Subject (whether the Subject is male or female).
6. Necessitates medical or surgical intervention to preclude permanent impairment of a body function or permanent damage to a body structure.
7. Important medical events that may not result in death, are not life-threatening, or do not require hospitalization may also be considered SAEs when, based upon appropriate medical judgment, may jeopardize the Subject and may require medical or surgical intervention to prevent one of the outcomes listed in this definition. Examples of such medical events include blood dyscrasias or convulsions that do not result in inpatient hospitalization, or the development of drug dependency or drug abuse.

An inpatient hospital admission in the absence of a precipitating, treatment-emergent, clinical adverse event may meet criteria for "seriousness" but is not an adverse experience, and will therefore, not be considered an SAE. An example of this would include a social admission (Subject admitted for other reasons than medical, e.g., lives far from the hospital, has no place to sleep).

A serious, suspected adverse drug reaction is an SAE that, in the opinion of the site Investigator or Sponsor, suggests a reasonable possibility that the investigational product caused the event.

The site Investigator is responsible for classifying adverse events as serious or non-serious.

10.3 Assessment and Recording of Adverse Events

This study will utilize the CTCAE version 4.0 coding system for adverse event recording. Adverse events reported using CTCAE will be recoded into MedDRA terms by the DCC.

10.3.1 Assessment of Adverse Events

At each visit (including telephone interviews), the Subject will be asked "Have you had any problems or symptoms since your last visit?" in order to determine the occurrence of adverse events. If the Subject reports an adverse event, the Investigator will determine:

1. Type of event
2. Date of onset and resolution (duration)
3. Severity (mild, moderate, severe)
4. Seriousness (does the event meet the above definition for an SAE)
5. Causality, relation to investigational product and disease
6. Action taken regarding investigational product
7. Outcome

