Irritability in HD can be understood as excessive emotional responsiveness or emotional dyscontrol, analogous in many ways to the motor dyscontrol that is pathognomonic for the disorder. Irritability is experienced as episodic, periodic, or chronic internal feelings of anxiety, impatience, and anger and can be manifest externally by being short tempered, impulsive, impatient, volatile, hostile, abusive, agitated, angry, aggressive, and violent. Internal physiological and mental stresses as well as external stresses typically trigger or exacerbate irritability with the reactions often seeming out of proportion to the stressors. Triggers for irritability may not be evident, making environmental modification and behavioral interventions challenging. Patients with HD commonly have limited awareness of the frequency and magnitude of their irritability, may feel that it is justified by circumstance, or may deny it. Since irritability leads to negative actions, interactions and secondary consequences, it can be self-reinforcing, cause others to modify their behavior to avoid exacerbations, contribute to conflict and isolation, and lead to behavior destructive to the environment, to self, and to others, and thus to social, medical, legal, and law enforcement constraints and complications. Its impact on HD families cannot be overstated, since it terrifies those who are at risk for developing HD and drives away caregivers and potential supporters in the community. Irritability and its consequential behaviors are one of the main contributors to use of highly sedating medications and to institutionalization.

Despite the frequent occurrence and severe consequences of irritability, including anger and aggression in HD, the development of specific therapies for these problems has received little attention to date (Thompson 2012).

A review of the literature shows there have been no placebo controlled, randomized treatment studies for irritability in HD (Groves 2011, van Duijn 2010). Irritability is common in

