11. Availability of a responsible Study Partner who has good English skills, is familiar with the Subject, and is able and willing to comply with all required study procedures, ensuring that the Subject attends all study visits and takes the study medicine as instructed. The Study Partner must spend time with the Subject a minimum of 4 times per week on 4 separate days, and must monitor the Subject's compliance and adverse events, participate in Study Partner assessments, and use the eDiary.
12. Subject has provided written, informed consent or, if Subject lacks the capacity to provide informed consent, a legally authorized representative (LAR) has provided written informed consent and the Subject has provided assent.

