6.3 Visit 01 (Week 2) Day 14±5

The following procedures will be performed during this visit (this visit may take about 2 hours):

- Assess the Subject for possible AEs and Concomitant Medication use.
- Review amount of study drug returned and assess compliance.
- Review the use of the eDiary and encourage the Subject and Study Partner to make and upload entries two times per day.
- Perform orthostatic vital sign measurements: blood pressure (systolic and diastolic) and heart rate (beats/minute).
- Record the Subject's body temperature (°C).
- Perform a resting 12-Lead EKG.
- Perform clinical assessment for suicidal ideation with the CSSRS.
- Collect blood samples for routine hematology/serum chemistry (refer to Section 6.13.5 for required tests).
- If two tubes not collected at Baseline Visit (Day 0), collect blood samples for CAGn genotyping and/or DNA storage (refer to University of Rochester Medical Center Lab Manual for sample handling and processing requirements).
- Collect urine for routine urinalysis (refer to Section 6.13.5 for required tests).

- Dispense study drug and instruct the Subject and Study Partner about correct administration of study drug (i.e., change in dose to 120 mg BID SRX246 or Placebo).
- Instruct Subject and Study Partner to bring unused study drug to each study visit, and to immediately report any AEs to the Investigator or Coordinator.

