6.4 Visit T1 (Week 4) Day 28±5

This visit will be a Telephone follow-up to perform the following (this may take about 15 minutes):

- Assess the Subject for possible AEs and Concomitant Medication use.
- Inquire about study drug compliance - assess whether study drug is being taken properly by the Subject (and if applicable, Study Partner) self-report. Subjects who do not experience intolerance will remain on their daily dose of study drug.
- Instruct Subject and Study Partner to bring unused study drug to each study visit, and to immediately report any AEs to the Investigator or Coordinator.
- Review the use of the eDiary and encourage the Subject and Study Partner to make and upload entries two times per day.

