Study participants who sign consent and receive investigational treatment will be monitored for AEs from the time they sign consent through week 12 or the end of their study participation. This study utilized the CTCAE version 4.03 coding system for AE recording. AEs reported using CTCAE will be recoded into MedDRA terms by the DCC.

At each visit, the participant will be asked "Have you had any problems or symptoms since your last visit?" in order to determine the occurrence of AEs. If the study participant reports an AE, the Investigator will determine:

- Type of event
- Date of onset and resolution (duration)
- Severity (mild, moderate, severe, life-threatening, results in death)
- Seriousness (does the AE meet the definition of an SAE)
- Causality, relation to investigational product and disease
- Action taken regarding investigational product
- Outcome

All clinical AEs are recorded in the AE data entry template in the study participant's study binder. The sites should fill out the AE data entry template and enter the information into the Online Adverse Event Reporting System (AERS) within 5 working days / 7 calendar days of the site learning of a new AE or receiving an update on an existing AE. Entries in the AE data entry template will include the following:

- Name and severity of the AE
- Date of onset
- Date of resolution

- Relationship to study drug
- Action taken
- Primary outcome of event

The severity of all AEs will be graded according to CTCAE, version 4.03. Any AE not listed in the CTCAE will be graded as follows:

- Grade 1 – Mild: Transient or mild discomfort; No limitation in activity; No medical intervention/therapy required
- Grade 2 – Moderate: Mild to moderate limitation in activity; Some assistance may be needed; No or minimal medical intervention/therapy required
- Grade 3 – Severe: Marked limitation in activity, some assistance usually required; Medical intervention/therapy required; Hospitalizations possible
- Grade 4 – Potentially Life-Threatening: Extreme limitation in activity; Significant assistance required; Significant medical intervention/therapy required; Hospitalization or hospice care probable
- Grade 5 – Death: The AE results in death

The Site Investigator is initially responsible for classifying AEs as serious or non-serious. An AE is considered serious if it meets one or more of the following criteria:

- Results in death

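### The scheduled AE question goes to the Subject but not to the Study Partner who must monitor AEs, so some behavioural AEs may be missed

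*Protocol*

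**What the plan says.** Both documents address the scheduled AE question to the Subject. Protocol 10.3.1 reads "At each visit (including telephone interviews), the Subject will be asked", and the follow-up has the same trigger: "If the Subject reports an adverse event, the Investigator will determine". SAP 3 reads "At each visit, the participant will be asked". The visit instructions in Protocol 6.3 to 6.9 carry one AE line, "Assess the Subject for possible AEs and Concomitant Medication use", with no matching line for the Study Partner.

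Three other parts of the protocol bear on this:

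- **Insight.** Section 2.1 states: "Patients with HD commonly have limited awareness of the frequency and magnitude of their irritability". It adds that they may think the irritability justified, or deny it. Eligibility (Section 4.1) extends down to a TFC of 5 and to Subjects for whom a legal representative consents.
- **The Partner's duty.** Under inclusion criterion 11 the Partner "must monitor the Subject's compliance and adverse events, participate in Study Partner assessments".
- **What counts.** Section 7 treats irritability, aggression, depression and suicidality as expected AEs. At grade 2 and above it requires a documented decision on referral or acute intervention. Section 10.1 keeps outcome-measure results out of AE recording.

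**The concern.** The plan solicits AEs at every contact from the informant it describes as commonly unaware of irritability. From the informant it requires to watch for AEs, it relies on volunteered reports. The week 4 call shows that the Partner can be asked: for compliance, staff are to "assess whether study drug is being taken properly by the Subject (and if applicable, Study Partner) self-report". The AE line of the same call mentions only the Subject.

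Two things are at stake. An unrecorded behavioural AE does not enter the safety tables, including the comparisons by MedDRA system organ class in SAP 8. It also does not start the documented referral decision in Protocol Section 7, which presupposes that the event has been noticed and graded.

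**Working it through.** No figure in the plan bears on this, so the check sets the passages side by side and then asks which summaries a missed event can change.

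**Step 1: who is asked, contact by contact (Protocol 6.3 to 6.9)**

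| Contact | AE line addressed to | AE question to Partner | Partner told to report AEs | Partner-informed scales |
|---|---|---|---|---|
| Week 2 (6.3) | Subject | none | yes | none |
| Week 4 call (6.4) | Subject | none | yes | none |
| Week 6 (6.5) | Subject | none | yes | yes |
| Week 8 (6.6) | Subject | none | yes | none |
| Week 10 (6.7) | Subject | none | yes | none |
| Week 12 (6.8) | Subject | none | yes | yes |
| Follow-up call (6.9) | Subject | none | no | none |

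All seven contacts after Baseline assess the Subject for AEs, and none schedules an AE question to the Partner. Six of the seven repeat the instruction to report AEs, which is also given at Baseline (6.2). Partner-informed scales are given at two of the seven.

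**Step 2: do other Partner data fill the gap?** Scale results are not recorded as AEs (10.1). The Partner answers daily eDiary questions on irritability and behaviour (Section 3), but no text routes those answers to AE recording. Partner attendance in person is encouraged rather than required (4.4.4).

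**Step 3: which summaries can change?** For arm *k*, let

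- *b_k* = proportion with at least one behavioural AE,
- *u_k* = proportion whose only AEs are behavioural, so *u_k* ≤ *b_k*,
- *m* = share of such participants in whom every behavioural AE goes unrecorded, taken as equal across arms and groups (an assumption; blinding makes equality across arms plausible).

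Then:

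- Any-AE endpoint: recorded proportion = true proportion − *m·u_k*. A participant with any other recorded AE is still counted.
- Behavioural events alone: recorded proportion = (1 − *m*)·*b_k*, and the difference between arms becomes (1 − *m*)(*b_drug* − *b_placebo*), closer to zero whichever arm has more.

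Since *m·u_k* ≤ *m·b_k*, the loss in each arm is never larger for the any-AE endpoint than for behavioural events alone. A system organ class that also holds other events lies between the two. The documents give no value for *m*, *u_k* or *b_k*, so this yields direction and ordering but no size.

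**The case against.** The strongest reply is that the scripted question is only one route. The Partner must monitor AEs as a condition of entry and is told to report them at once from Baseline through Week 12. The Partner can also request an unscheduled visit or call, for which behavioural worsening is a listed reason (6.10). Sites must document how they handle emergency calls from a care partner (Section 7). Section 10.3.5 covers events reported to or observed by site staff, without limiting who reports. Examination findings, vital signs and laboratory tests count too (10.1; SAP 3). At Weeks 6 and 12 the PBA-s interview takes the Subject and Partner together through irritability, aggression and mood.

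All of that stands, and it rules out several stronger readings:

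- **That AEs come only from the Subject, or that the safety endpoint hangs on one question.** This is true of the scheduled question but not of AE capture.
- **That behavioural AEs will be under-counted.** The documents show a route by which events may be missed, but not that they are, or how often.
- **That the any-AE difference shrinks in proportion to the miss rate.** Step 3 shows that only participants with no other recorded AE are affected.
- **That under-recording would decide the non-inferiority result.** SAP 8 defines the difference as placebo minus treatment for AE proportions too, so an excess on drug moves it away from the 0.5 threshold however well events are captured. That is a separate matter, and this point does not rest on that test.
- **That these are the AEs of most concern for this drug.** The events listed from earlier studies (Protocol 2.3 and 7) are tachycardia, gastrointestinal symptoms and a few others. Section 7 attributes the behavioural symptoms to HD.

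The reply does not explain why the Subject, who gets the same instruction to report, is nevertheless asked at every contact while the Partner is not.

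**Conclusion.** The point holds as a modest weakness in how AEs are elicited. In both documents the scheduled question goes to the Subject alone, and the Partner's required monitoring of AEs has no scheduled question to collect its result. Some behavioural AEs may be missed as a consequence.

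The size is unknown. The any-AE endpoint is partly protected because any other recorded AE keeps the participant in the count. The system organ class comparisons and the grade 2 and above referral decision have less protection. The tendency of behavioural differences to shrink towards zero assumes roughly equal under-recording across arms. How much spontaneous Partner reporting recovers cannot be judged from the documents.

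**What to change.** In Protocol 10.3.1 and the AE lines of Sections 6.3 to 6.9:

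- Put the same AE question about the Subject separately to the Study Partner at every visit and call, by phone if the Partner is absent. Section 4.4.4 already allows Partner assessments by phone.
- Let a report from either informant start the Investigator's determination, and count an AE reported by either.
- Record the source of each AE.

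Align SAP 3 with this wording. SAP 1 describes randomization and visits in the past tense, so the elicitation may no longer be open to change. If data collection has ended, state in the SAP that AEs were solicited on schedule from the Subject only, and that behavioural AE counts should be read with that limitation.

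The cost is wording changes and a few minutes per contact with someone already consented and reachable. No extra staff or procedures are needed. The downside is somewhat more AE reports in every arm.

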10.3.2 Relatedness of Adverse Event to Investigational Product

The relationship of the AE to the investigational product should be specified by the site Investigator, using the following definitions:

1. Not Related: Concomitant illness, accident or event with no reasonable association with treatment.
2. Unlikely: The reaction has little or no temporal sequence from administration of the investigational product, and/or a more likely alternative etiology exists.
3. Possibly Related: The reaction follows a reasonably temporal sequence from administration of the investigational product and follows a known response pattern to the suspected investigational product; the reaction could have been produced by the investigational product or could have been produced by the Subject's clinical state or by other modes of therapy administered to the Subject. (suspected ADR)

4. Probably Related: The reaction follows a reasonably temporal sequence from administration of investigational product; is confirmed by discontinuation of the investigational product or by re-challenge; and cannot be reasonably explained by the known characteristics of the Subject's clinical state. (suspected ADR)
5. Definitely Related: The reaction follows a reasonable temporal sequence from administration of investigational product; that follows a known or expected response pattern to the investigational product; and that is confirmed by improvement on stopping or reducing the dosage of the investigational product, and reappearance of the reaction on repeated exposure. (suspected ADR)

